The Erasmus MC radiotherapy department treats approximately 5500 patients per year. Roughly 2000 patients are treated with palliative intent, which means that these are patients with metastasized cancer, who need to be irradiated to relieve complaints and/or improve their quality of life of their final stage of life. A large portion of the patients are treated for painful bone metastases at the dedicated outpatient clinic at the Erasmus MC radiotherapy department.

The current radiotherapy workflow consists of a treatment preparation and a treatment delivery phase. At the dedicated outpatient clinic, patients are treated at the same day they had their intake or, if patients prefer, the day after. This means that the regular preparation phase of multiple days (up to a week) is reduced to less than a day (typically 3 to 6 hours in total). During the preparation phase a CT scan of a patient is acquired. This CT-scan is used to delineate the target volume and the organs at risk. Based on this information a patient specific treatment plan is generated. During the treatment delivery phase (approx. 15 minutes) it is very important that the patient is positioned according to the CT-scan. Therefore patients are positioned on an uncomfortable hard flat table top during both treatment phases. To somewhat improve the comfort for this patient group a thin mattress (not labeled as a medical device) is added during the normal clinical routine.

To increase comfort and relieve the pain during the CT-scan and treatment delivery a thicker mattress was developed together with Royal Health Foam, and 6 samples were produced. These mattresses are no medical devices, since any effect they may have on the treatment is negligible. No special guidelines are available for these kind of mattresses. All mattresses were approved for standard clinical practice by the responsible medical physicist using the appropriate procedures at the department of radiotherapy. These procedures included radiation transmission measurements, ease of use and cleaning and phantom measurements to quantify the sag of the mattresses.

Objective(s)

Please specify the main and secondary objectives of the study.

The primary objective is to determine if patients find the (newly developed) thicker radiotherapy mattress more comfortable than the standard thin matrass.

The secondary objectives are:

- 1. To determine if patients who experience pain while lying on any of the matrasses find the thicker radiotherapy matrass more comfortable than the standard thin matrass.
- 2. To determine if the patient experience less pain while lying on the thick matrass compared to while lying on the thin matrass
- 3. To record patient motion during treatment using the optical surface monitoring which is already used in routine clinical practice

Study type

Please describe the design of the study.

A prospective observational study

Study population

Please describe the study population, e.g., healthy volunteers, xx year old.

Only patients (age ≥ 16) with bone metastasis in thoracic, abdominal and pelvis region who are treated at the one-stop shop for palliative radiotherapy are included in this study. The total number of patients that will be included is 45. See section 4.5 for more details.

Methods

Please describe how you conduct research and which methods are used.

The study will be discussed with the patient by the treating physician during intake, or right after by a radiotherapy technologists (RTT). For patients that sign the informed consent, prior to planning-CT acquisition, patients will be asked to lie on each mattresses for 1 minute. Next patients are asked to score the pain they experienced, on a scale of 0-10 while lying on each mattress. Also patients are asked which mattress they prefer. Next the CT scan is acquired of the patients lying on the mattress of choice. The same mattress will also be used during irradiation. Note that both mattresses have been released for clinical use, and the choice of mattress does not affect the quality of the treatment. Only potentially the experienced comfort.

Right before start of treatment and in line with clinical practice, patients will be positioned on the treatment couch with the aid of the optical surface monitoring system. The optical surface monitoring system makes a 3D scan of the surface of the patient from which it calculates the motion (3 translations, 3 rotations) of a predefined region of interest. During treatment, the quality of the treatment is evaluated based on the motion information, and if necessary, RTTs could pause the delivery. Specifically for the study, the motion of the patient will be assessed in more detail after treatment.

Burden and risks

Please describe the burden and risks associated with participation.

There is no additional risk introduced by the treatment on thick mattress.

The burden of the patient is limited to testing the mattress prior to CT-acquisition and scoring of its comfort. Which takes about 5 minutes. Both mattress are suitable for the radiotherapy treatment. So the choice of mattress does not affect the treatment.

Recruitment and consent

Please describe the recruitment and informed consent procedures.

Patients will be asked to sign informed consent by the radiation oncologist during intake or by the RTT right after intake.

1. Introduction and rationale

Please specify background and hypothesis (if applicable) of the study.

Together with Royal Health Foam, the department of Radiotherapy developed a new mattress, which could replace the thin mattresses that are currently in use for patient positioning during treatment. The only purpose for this mattress is to offer comfort to patients, that are treated on a flat treatment couch at the radiotherapy treatment machine. To improve the comfort of the mattress, the new mattress is thicker than the mattress currently in use. Especially for patients that are treated with palliative intent who are often frail and in pain, it is expected that the thick mattress could provide a more comfortable treatment experience.

Because the thick mattress should not interfere with the dose delivered by the treatment machine, the thick mattress is made of dedicated materials. Although the thick mattress is not considered a medical device, all samples were evaluated for safe use in the clinic in terms of radiation transmission, and ease of use and cleaning. Also the positioning stability of a phantom and two volunteers on the mattress was assessed and within tolerances. After which the mattress has been approved for clinical use at the department of radiotherapy.

2. Objective(s)

The objectives of the study are the questions that the study is intended to answer and are based on the scientific rationale and/or hypothesis formulated.

Please specify the main and <if applicable> secondary objective(s) of the study.

The primary objective is to determine if patients find the thicker radiotherapy mattress more comfortable than the standard thin matrass.

The secondary objectives are

- 1. To determine if patients who experience pain while lying on any of the matrasses find the thicker radiotherapy matrass more comfortable than the standard thin matrass.
- 2. To determine if the patient experience less pain while lying on the thick matrass compared to while lying on the thin matrass
- 3. To record patient motion during treatment using the optical surface monitoring device that is used in routine clinical practice for patient positioning.

3. Study type

3.1. Study type

	□ Retrospective □ Prospective □ Combination Retrospective/Prospective
3.2.	Single center / Multicenter
	☑ Single center☐ Multicenter

3.3 Check all the applicable boxes

☐ Case report
☐ Re-use data from research
☐ Evaluations of quality of healthcare (retrospective)
☐ Research with additional use of residual material from regular healthcare
☐ Research with re-use of human material from research or existing biobank
☐ De novo biobank
☐ Phase IV research
☑ Healthcare evaluation research (prospective)
☐ Research with medical devices
☐ Research with In Vitro Diagnostic Tests
□ Other research, describe

4. Study population

4.1. Study population

☑ Adults (16 years and older)
☐ Minors (younger than 16 years)
☐ Incapacitated adults (16 years and older)
☐ Incapacitated minors (younger than 16 years)

4.2. Population (base)

Describe the population (patients and controls if applicable), e.g. healthy human volunteers, xx-xx year old, adults, minors and/or incapacitated adults or minors. Specify and justify the number of subjects required for the study.

Patients that are treated at the one-stop shop at Erasmus MC for palliative radiotherapy. For the required number of patients see section 4.5

4.3. Inclusion criteria

In order to be eligible to participate in this study, a subject must meet all of the following criteria:

- Age: ≥ 16
- Patients treated for bone metastasis in thoracic, abdominal and pelvic region
- Patients have read, understood and signed the informed consent of the COMFORT study.

4.4. Exclusion criteria

A potential subject who meets any of the following criteria will be excluded from participation in this study:

Patients not willing or able to test two mattresses (regular and thicker)

4.5. Sample size calculation

Specify and justify the number of subjects required for the study, estimated number of subjects, or number of subjects in the period of evaluation.

The estimated number of patients needed for evaluation of mattress preference is 36. This number is calculated for a one-sample proportions z-test with an estimated preference for thick mattress of 70%, with ±15% error margin and a confidence level of 95%. These power calculations were performed by [name], statistician at Erasmus MC.

For some patients the optical surface monitoring system may not be able to accurately detect the body of the patients, for instance due to too much body hair. These patients will be included for the primary objective, but cannot be evaluated for the third secondary objective. To account for these patients, accrual will continue until either 36 patients are included that can be evaluated for all objectives or a maximum number of total patients of 45.

5. Methods

[figure not shown]

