7.1 Main study parameters/endpoints

Describe how data will be analyzed

Please describe the main study parameters/endpoints.

The percentage of patients that preferred the thick mattress

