7.4 Analysis

Please describe how the analysis will be done for the outcome parameters.

- The mattress preference is calculated as the fraction of patients that preferred the thick mattress: number of patients who chose the thick mattress / the total number of patients included. Also the confidence intervals will be investigated.
- The experienced comfort per mattress is calculated as the average of the patients' scores.
 Also the distribution of the scores per group (preference for thin vs thick mattress) and confidence intervals will be investigated
- The experienced pain per mattress is calculated as the average of the patients' pain scores.
 Also the distribution of the scores per group (preference for thin vs thick mattress) and confidence intervals will be investigated
- The motion is defined by the translation (in 3D) measured by the AlignRT® camera system, after exclusion from the breathing motion based on a fast Fourier transform.

8. Ethical considerations

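### Does calling n = 36 a z-test power calculation in section 4.5, with no test or decision rule in section 7.4, leave the primary question without a sound answer?

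*Combined protocol and SAP*

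**What the plan says.** The primary objective (Summary and section 2) is put as a yes/no question: "The primary objective is to determine if patients find the thicker radiotherapy mattress more comfortable than the standard thin matrass". The main endpoint in section 7.1 is a single proportion: "The percentage of patients that preferred the thick mattress".

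Section 4.5 sets the size: "The estimated number of patients needed for evaluation of mattress preference is 36". It explains the figure by "This number is calculated for a one-sample proportions z-test with an estimated preference for thick mattress of 70%, with ±15% error margin" and a 95% confidence level, and then says "These power calculations were performed by" a statistician at the centre. Accrual runs until 36 patients are evaluable for every objective, or until 45 in total. Of patients whose surface monitoring fails, it says "These patients will be included for the primary objective, but cannot be evaluated for the third secondary objective". The primary analysis may therefore contain anywhere from 36 to 45 patients.

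Section 7.4 defines the estimate as the number choosing the thick mattress divided by the number included, and adds "Also the confidence intervals will be investigated". It names no test, interval method, reference value or criterion.

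**The concern.** Two things look wrong on a first reading.

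- **The label.** A power calculation for a one-sample z-test needs a null proportion, a sidedness and a power. Section 4.5 gives none of these. A reader could come away believing that the study was powered, at some conventional level, to show a preference for the thick mattress.
- **The missing rule.** The objective asks whether the thick mattress is found more comfortable, but the test named in section 4.5 does not reappear in section 7.4, and nothing says how the interval is to be turned into a yes or no. If the interval method were picked after seeing the data, a borderline count could be read either way. The primary conclusion would then rest on a choice made with the result in view.

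**Working it through.** **1. Reproduce the plan's figure.** Inputs from section 4.5: p = 0.70, margin d = 0.15, 95% confidence (z = 1.96).

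n = z² p(1 − p) / d² = 1.96² × 0.7 × 0.3 / 0.15² = 35.85, rounded up to **36**.

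This is the precision formula, and it matches exactly. The half-width at 70% is 1.96 × √(0.21/36) = 15.0 points at n = 36 and 1.96 × √(0.21/45) = 13.4 points at n = 45. The Wilson half-widths are 14.4 and 12.9.

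**2. Could 36 be a z-test figure?** Reading the 15 points as a test difference, 55% against 70% at 5% significance and 80% power needs 83 patients two-sided or 65 one-sided; 70% against 85% needs 64 or 50. The nearest conventional design is 50% against 70%, one-sided 5%, 80% power, which gives 36.49, so 37. That needs a null and a power that the plan does not state, and it leaves the ±15% unused. The precision reading is the one that uses all the stated inputs and nothing else.

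**3. How much can the choice of interval matter?** Assumption: the natural reference for a choice between two mattresses is 50%, and a preference is read from a 95% lower limit above it. The documents do not state this value. The table gives the smallest number choosing thick that puts the lower limit above 50%, and the binomial probability of a count on which the methods disagree if the true preference is 70%.

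| n | Simple z-based | Wilson | Exact | Chance of a disputed count |
|---|---|---|---|---|
| 36 | 24 | 24 | 25 | 12.7% |
| 37 | 25 | 25 | 25 | 0 |
| 38 | 25 | 26 | 26 | 11.6% |
| 39 | 26 | 26 | 27 | 12.2% |
| 40 | 26 | 27 | 27 | 10.4% |
| 41 | 27 | 27 | 28 | 11.1% |
| 42 | 28 | 28 | 28 | 0 |
| 43 | 28 | 28 | 29 | 10.0% |
| 44 | 29 | 29 | 29 | 0 |
| 45 | 29 | 30 | 30 | 9.0% |

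The methods never differ by more than one patient. If the true preference is 50%, the chance of a disputed count is at most 2.1% (n = 40).

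**4. What a disputed count looks like.** Lower 95% limits (simple z-based, Wilson, exact):

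- 24/36 (66.7%): 51.3%, 50.3%, 49.0%. Disputed.
- 25/36 (69.4%, close to the planned 70%): 54.4%, 53.1%, 51.9%. All agree.
- 29/45 (64.4%): 50.5%, 49.8%, 48.8%. Disputed.
- 30/45 (66.7%): 52.9%, 52.1%, 51.0%. All agree.

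Even at the disputed counts the intervals differ by about two points or less at the lower end. Any reader shown the fraction and any of the three would see a result on the edge of 50%.

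**5. Would fixing a method be a clear gain?** At n = 36 the Wilson rule (24 or more) has a true two-sided size of 6.5% and power of 74% at a true 70%. The exact rule (25 or more) has a size of 2.9% and power of 61%. Neither dominates the other.

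**The case for a change.** The strongest case for a change is that the objective is worded as a decision while the plan offers only a description. The three common intervals set different thresholds at 7 of the 10 possible final sizes, and the results where they differ are those in which a rule chosen after the fact is least credible. Against an assumed 50% null and a true 70%, two-sided power at n = 36 is only 61% (exact), 68% (normal approximation) or 74% (z-test by enumeration), which a reader of the words power calculation might not expect. The remedy would be a few words in two sections.

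Much of this stands as fact. The label in section 4.5 is wrong, and no passage elsewhere supplies the null, the interval method or the criterion. The claimed harm does not follow from it. The power figures depend on a null, a sidedness and a test that the plan never adopts; at one-sided 5% the same design gives 74% to 84%. If 36 is a precision figure, as the arithmetic shows, modest power for an unplanned test is not a failing of the design. The interval choice affects one borderline count at some sizes. That is well short of letting the same data generally be read either way.

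**Conclusion.** The observation is accurate, but it does not call for a change. Section 4.5 mislabels a precision calculation. The number 36 is right for a 95% half-width of 15.0 points at 70%, improving to 13.4 at 45 patients, and relabelling it would alter no patient count and no result. Section 7.4 omits detail that its reader can supply: sections 4.5 and 7.4 taken together imply a 95% interval for one proportion, 50% is the evident reference for a two-way choice, and the planning values of 70% ± 15 points (55% to 85%) lie above it. Reported that way, the primary result supports a sound conclusion.

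The remaining exposure is at most one disputed count per final size, with a probability of 0 to 12.7% at a true preference of 70% and at most 2.1% at 50%. These figures assume the 50% reference, a two-sided 95% interval, independent patients and a fixed final size between 36 and 45. Choosing between Wilson and exact trades size against power and corrects no error. The setting also makes an estimate with its interval a reasonable primary analysis: this is a single-centre healthcare evaluation of two mattresses already released for clinical use.

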5.1. Research methods

Please describe how you conduct research and which methods are used, e.g., questionnaires, human material collection, extraction of data from medical records, analysis of images, the use of an app/medical device/diagnostic test, clinical tests to be performed, etc. Include information

on frequency, duration, volumes. If a Data Management Plan is available, please upload DMP.

Included patients are asked to test the regular and thick mattress for 1 minute each, right before CT scanning. Directly after testing each mattress, patients are asked to score whether they experienced pain lying on any of the mattress (score 0-10) and asked which mattress they prefer. Next the CT scan will be acquired with the mattress of choice. Note that the choice of mattress does not affect the quality of the treatment.

In line with clinical routine, right before treatment, the positioning of the patient on the treatment couch is assessed using an optical surface scanning system. The system acquires a 3D scan of the surface of the patient to verify the patient position right before treatment. To evaluate the quality of the treatment, the patient potion during treatment is also monitored by the same system. Of the 3D surfaces scans that are acquired over time during treatment, only the 3D motion (3 translation and 3 rotations) will be assessed. In the figure below the 3D surface is indicated in white, with the predefined region of interest in yellow. The average motion is shown as the white curve within the green rectangle. All data is stored as radiotherapy treatment information in the context of the treatment. For the research, however, only the 3D motion will be assessed. Next the motion vector will be post-processed using a fast Fourier transform to filter out the breathing motion.

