5.4. Medical device(s) / In vitro diagnostic tests

Describe which medical device and/or in vitro diagnostic test is used, what the intended use of the medical device is and whether the medical device/diagnostic test is already available in the participating centers.

Both mattresses are not considered to be a medical device. They are not part of the treatment machine, can be safely omitted and their impact on the dose delivery is negligible.

Note here that this study is similar to the example about randomized studies at the CCMO website (https://english.ccmo.nl/investigators/legal-framework-for-medical-scientific-research/your-research-is-it-subject-to-the-wmo-or-not). This example describes a study on the prevention of decubitus, where subjects are randomized to the use of mattress A or B in their bed. Within the context of the WMO no rule of conduct is imposed in this example, and the use of another mattress is not considered as an infringement of the physical and/or psychological integrity of the subject. The website concludes that such randomized studies are not subject to the WMO, providing that no other procedures or rules of behavior are imposed (for instance taking blood samples). Note that he current study does not even randomize.

6. Incidental findings

	6.1.	Chance of incidental findings Is there a chance of incidental findings? ☐ Yes ☑ No
	6.2.	Procedures If yes, describe who will be notified and how the subjects and other parties will be notified in case of incidental findings from the study that may be in the interest for the participant's health.
		Not applicable.
7.	Stati	stical analysis

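### The order in which each patient tests the two mattresses is neither balanced nor mentioned as recorded, so an order effect could bias the primary preference share

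*Combined protocol and SAP*

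**What the plan says.** The Methods part of the Summary states that "patients will be asked to lie on each mattresses for 1 minute". Section 5.1 repeats this: "Included patients are asked to test the regular and thick mattress for 1 minute each, right before CT scanning". Pain scores and the preference are collected straight after the tests. The chosen mattress is then used for the scan: "Next the CT scan will be acquired with the mattress of choice".

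The primary endpoint in section 7.1 is "The percentage of patients that preferred the thick mattress". Section 7.4 computes it as "number of patients who chose the thick mattress / the total number of patients included" and adds "Also the confidence intervals will be investigated", without naming a method. Pain and comfort are handled in the same way, as averages per mattress: "The experienced pain per mattress is calculated as the average of the" patients' scores. Nothing is analysed by test order.

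Test order does not appear among the other parameters (7.3: treatment site and weight) or in the data list (9.1). Section 5.4 remarks "Note that he current study does not even randomize". In context this concerns allocation to a mattress, but no other section adds a randomised or alternated test order. Section 16 ticks questionnaires as an attachment. They are not part of the text available here and may include a field for order.

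**The concern.** This is a within-patient comparison of two items tried one after the other, with a subjective choice as the outcome. A patient may favour whichever mattress came last, or may be more tired or sore by the second test. The plan leaves the order open, so staff habit or convenience decides it. If one order dominates, the order effect and the mattress effect cannot be separated.

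The primary share, and the pain and comfort averages that come from the same two tests, could then move for a reason unrelated to the mattress. A confidence interval does not show this kind of bias, and more patients do not reduce it. If the order is not recorded either, it cannot be examined afterwards.

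**Working it through.** **Inputs from the plan (section 4.5).** Expected thick preference 70%, margin ±15 points, 95% confidence, N = 36, maximum 45.

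**The plan's own figure.** n = 1.96² × 0.70 × 0.30 / 0.15² = 35.9, rounded up to 36. The stated N reproduces and is not in dispute.

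**Assumed inputs (not in the documents).** The mattress tested second gains d, so P(choose thick) is 0.70 + d when thick is second and 0.70 − d when thick is first. The contrast between the two orders is 2d. Let f be the share of patients testing thick second. The true value is taken as the mean of the two orders, 0.70.

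**Bias.** Expected share = f(0.70 + d) + (1 − f)(0.70 − d) = 0.70 + d(2f − 1), so the bias is d(2f − 1).

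- d = 0.05, all thick second (f = 1): +5 points.
- d = 0.05, all thick first (f = 0): −5 points.
- d = 0.05, 29 of 36 thick second: 0.05 × (58/36 − 1) = +3.1 points.
- 18/18 (f = 0.5): 0 for any d.
- n = 45 split 23/22, d = 0.05: 0.05 × 1/45 = 0.1 point.

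**Coverage of the true 70% by a 95% interval.** The number choosing thick is Bin(n₂, 0.70 + d) + Bin(n₁, 0.70 − d), where n₂ patients test thick second and n₁ test it first. Coverage is the probability of those counts whose interval contains 0.70. Several interval types are shown because the plan names none.

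| n | Thick second | d | Bias (points) | Wald | Wilson | Exact |
|---|---|---|---|---|---|---|
| 36 | any | 0 | 0 | 92.4% | 95.6% | 95.6% |
| 36 | 36 | 0.05 | +5 | 82.8% | 91.3% | 91.3% |
| 36 | 0 | 0.05 | −5 | 89.9% | 90.7% | 90.7% |
| 36 | 29 | 0.05 | +3.1 | 88.3% | 94.3% | 94.3% |
| 36 | 36 | 0.10 | +10 | 59.9% | 75.3% | 75.3% |
| 36 | 18 | 0.05 | 0 | 92.6% | 95.8% | 95.8% |
| 36 | 18 | 0.10 | 0 | 93.1% | 96.1% | 96.1% |
| 45 | any | 0 | 0 | 93.9% | 95.1% | 96.6% |
| 45 | 45 | 0.05 | +5 | 82.6% | 90.2% | 90.5% |

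**Effect of more patients.** The half-width at 70% is 1.96 × √(0.21/n): 15.0 points at n = 36 and 13.4 at n = 45. With all patients in one order and d = 0.05 the bias stays at 5 points, so the interval tightens around the wrong value.

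**Precision within each order.** By the same formula, ±21 points at n = 18 and ±19 at n = 22 or 23.

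**The case against.** The harm needs two things the documents do not show: an order effect and a dominant order. The wording of the plan fits either order or a mixture. The modest case is mild. With Wilson or exact intervals, coverage is 91% even when every patient has the same order, and 94% at 29 of 36. The lower Wald figures partly reflect that Wald covers only 92% with no order effect at all. A 5-point bias is a third of the planned ±15 margin. The plan sets no null value or decision rule, so no changed conclusion can be shown, and nothing has been calculated for the pain and comfort averages. The unseen questionnaire may record order. The data list in 9.1 does not name the preference itself, so the absence of order from that list proves little. The remark about not randomising concerns allocation. A table by order could not reliably reveal a 10-point contrast: at 18 per order the difference carries about 1.96 × √(2 × 0.21/18) = ±30 points.

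Most of this stands as a limit on size and certainty. It does not remove the gap. Recording alone would not balance the order, and section 7.4 plans no use of it. The weakness of the table is a reason to balance in advance, because analysis at this sample size cannot repair an imbalance.

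**Conclusion.** The point holds, in conditional form. The visible plan leaves test order open, and the primary share is biased by d(2f − 1) if one order dominates and order matters. For an assumed 5-point gain to the second mattress and a single order throughout, the bias is 5 points in either direction. Coverage at n = 36 is then 91% with Wilson or exact intervals, and 83% (thick second) or 90% (thick first) with Wald. For an assumed 10-point gain with thick always second, it is 75% or 60%.

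These figures rest on an additive, symmetric order effect and a true share of 70%. The real size and direction of any order effect, and actual staff practice, are unknown. The sample size is unaffected. The point should be fixed because prevention is cheap and balance has to be built in as patients are tested.

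**What to change.** - **Section 5.1:** state that the order of testing (regular first or thick first) is assigned 1:1 per patient from a blocked list, and that the order actually tested is recorded. Blocking keeps the split close to even wherever accrual stops between 36 and 45.
- **Section 7.4:** keep the overall thick share with its 95% confidence interval as primary. Add one descriptive table of the thick share and the average pain and comfort scores by order, without a test or model.
- **Section 5.4:** reword the remark about not randomising so that it refers only to the choice of mattress.

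**Cost.** One list and one data field. N stays at 36 (maximum 45), and the patient still chooses. Technologists must follow a per-patient order.

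Some patients may need an extra mattress change before CT. The documents do not describe how mattresses are swapped. Assume testing on the CT couch, 70% choosing thick in either order, and a change whenever the first-tested mattress is chosen. The proportion needing a change is then 30% if thick is always second, 70% if thick is always first, and 0.5 × 30% + 0.5 × 70% = 50% when balanced.

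The amendment goes to the NWTC (section 12). The non-WMO argument in section 5.4 depends on no further procedures or behavioural rules being imposed, so the committee should confirm that randomising only the test order leaves it intact.
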